4.5 Progression to Respiratory Failure

Progression to respiratory failure is measured as the percentage of participants who progress to respiratory failure (i.e., need for mechanical ventilation, ECMO, non-invasive ventilation) by Day

The hypotheses to be tested are:

$$H_0: \pi_A = \pi_S \text{ versus } H_A: \pi_A \neq \pi_S$$

Let π_A and π_S represent the proportion of patients who have respiratory failure for Ampion and control during the first 28 days after randomization. This difference will be tested utilizing the appropriate chi-square test or Fisher's exact test utilizing PROC FREQ with the EXACT option, if needed. Also, the median time to respiratory failure will be tested for difference between the two groups via the log-rank test. The log-rank test will be performed using PROC LIFETEST; and the estimation of the time-to-event distributions will be performed using the method of Kaplan and Meier.

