#### 4.4 Inclusion Criteria

Patients should fulfill all the following inclusion criteria:

1. Male or female,  $\geq 18$  years old.
2. Diagnosed with COVID-19, as confirmed using a standard RT-PCT assay or an equivalent test.
3. Baseline severity categorization of severe or critical COVID-19 infection per FDA Guidance for developing drugs and biological products for COVID-19 (February 2021):
  - a) Severe COVID-19:
    - Symptoms suggestive of severe systemic illness with COVID-19, which could include shortness of breath or respiratory distress
    - Clinical signs indicative of severe systemic illness with COVID-19, such as respiratory rate  $\geq 30$  per minute, heart rate  $\geq 125$  per minute, SpO2  $\leq 93\%$  on room air or PaO2/FiO2  $\leq 300$
  - b) Critical COVID-19:
    - Oxygen delivered by high-flow nasal cannula (heated, humidified, oxygen delivered via reinforced cannula at flow rates  $> 20$  L/min with fraction of oxygen  $\geq 0.5$ ) or
    - Non-invasive mechanical or endotracheal mechanical ventilation
4. Informed consent obtained from the patient or the patient's legal representative.

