#### 4.5 Exclusion Criteria

Patients fulfilling one or more of the following criteria may not be enrolled in the study:

1. As a result of the medical review and screening investigation, the Principal Investigator considers the patient unfit for the study and/or progression to death is imminent and inevitable irrespective of the provision of treatments.
2. Clinical diagnosis of respiratory failure requiring ECMO and/or therapy is not available due to resource limitation.
3. Shock defined by systolic blood pressure  $< 90$  mm Hg, or diastolic blood pressure  $< 60$  mm Hg or requiring vasopressors.
4. Multi-organ dysfunction/failure.
5. Patient has severe chronic obstructive or restrictive pulmonary disease (COPD) (as defined by prior pulmonary function tests), chronic renal failure, or significant liver abnormality (e.g., cirrhosis, transplant, etc.).
6. Patient has chronic conditions requiring chemotherapy or immunosuppressive medication.
7. A history of allergic reactions to human albumin (reaction to non-human albumin such as egg albumin is not an exclusion criterion) or ingredients in 5% human albumin (N-acetyltryptophan, sodium caprylate).
8. Prolonged QT interval.
9. Patient has known pregnancy or is currently breastfeeding.
10. Patient planning to become pregnant, or father a child, during the treatment and follow-up period and/or is not willing to remain abstinent or use contraception.

11. Participation in another clinical trial (not including treatments for COVID-19 as approved by the FDA through expanded access, emergency, or compassionate use), or participation in a trial such that enrollment in this study would fall within the time frame of the half-life of the other investigational product(s).

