6.1.2 Intent to Treat (ITT) Analysis Set

The intent-to-treat (ITT) analysis population is defined as all randomized patients. All efficacy analyses will be performed in the ITT population. Patients will be analyzed as randomized.

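### The respiratory-failure test has no at-risk set and no rule for patients ventilated at entry or for deaths without ventilation, so its result depends on an unstated reading

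*SAP*

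**What the plan says.** - **Event.** SAP 4.5 describes the endpoint as the percentage who progress to respiratory failure ("i.e., need for mechanical ventilation, ECMO, non-invasive ventilation) by Day" 28). Protocol 3.3.2 and 9.4.2 and SAP 3.2 use the same event list. Death is not on it.
- **Tested parameter.** The next lines of SAP 4.5 define the two proportions as those that "represent the proportion of patients who have respiratory failure for Ampion and control during the first 28 days after randomization". The verb changes from *progress to* to *have*.
- **Analysis set.** SAP 6.1.2: "The intent-to-treat (ITT) analysis population is defined as all randomized patients", and "All efficacy analyses will be performed in the ITT population". Neither document defines an at-risk subset for this endpoint.
- **Entry criteria.** Protocol 4.4 admits critical patients on high-flow nasal cannula or on "Non-invasive mechanical or endotracheal mechanical ventilation". The nearest exclusion in Protocol 4.5 reads "Clinical diagnosis of respiratory failure requiring ECMO and/or therapy is not available due to resource limitation". It names ECMO and does not exclude ventilated patients.
- **Tests.** SAP 4.5 uses chi-square or Fisher's exact test for the proportions. It adds that "the median time to respiratory failure will be tested for difference between the two groups via the log-rank test", with no rule for death and none for patients already ventilated.
- **A second definition.** Protocol 5.2 (Intubation/Extubation) adds high-flow nasal cannula oxygen to the failure list. The other sections do not.

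**The concern.** A patient on a ventilator at randomisation already meets the event definition, so nothing that happens afterwards can show whether treatment prevented progression. The plan keeps such patients in the denominator and does not say how to score them. Two programmers following SAP 4.5 could code them in opposite ways, and the choice can decide the result.

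Death raises a separate issue. With an all-randomised denominator and an event list without death, a patient who dies without ventilation falls among the non-failures. If the arms differ in such deaths, the comparison can be weakened or turned towards the arm with more of them.

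Respiratory failure comes ahead of ICU admission and mortality in the hierarchical order of Protocol 9.4.2 and SAP 4. A diluted non-significant result here would stop formal testing of both.

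**Working it through.** **The plan's own figure.** Neither document gives a power figure for respiratory failure. The only sizing statement is for Day 28 mortality: 26% versus 8%, 100 per arm, at least 80% power. Using power = Φ{[|p₁−p₂| − z√(2p̄(1−p̄)/n)] / √[(p₁q₁+p₂q₂)/n]} with two-sided alpha 0.047 (z = 1.986) and p̄ = 0.17:

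(0.18 − 1.986 × 0.0531) / 0.0516 = 1.44, so power is 0.926 (0.909 by exact Fisher). The statement holds as a lower bound, but for a different endpoint.

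**Inputs for the respiratory-failure check.** From the documents: 100 per arm, 1:1, two-sided, final alpha 0.047. Assumed, because the documents do not give them: at-risk failure rates of 30% (control) and 12% (Ampion), and a share f ventilated at entry, equal in both arms.

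**Effect on the rates.**
- Counted as events: f + (1−f)p in each arm.
- Counted as non-events: (1−f)p in each arm.
- Risk difference in both cases: (1−f) × 0.18.

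For f = 0.30:
- Events: 0.30 + 0.70 × 0.30 = 51.0% versus 0.30 + 0.70 × 0.12 = 38.4%; ratio 0.75.
- Non-events: 21.0% versus 8.4%; ratio 0.40, the same as at risk.
- Risk difference 12.6 points instead of 18.

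For f = 0.10:
- Events: 37.0% versus 20.8%; ratio 0.56.
- Non-events: 27.0% versus 10.8%; ratio 0.40.
- Risk difference 16.2 points.

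**Power by exact Fisher.** With m = 100(1−f) at-risk patients per arm, power is the sum over i and j of Bin(i; m, 0.30) × Bin(j; m, 0.12) wherever Fisher's p ≤ 0.047. The 100f ventilated patients per arm are added as events, added as non-events, or left out.

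| Ventilated at entry | Counted as events | Counted as non-events | At-risk patients only |
|---|---|---|---|
| 10% | 69% | 80% | 80% |
| 30% | 33% | 65% | 68% |

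**Other assumed rates (normal approximation, alpha 0.047).** Borrowing 26% versus 8% as at-risk failure rates with 20% ventilated gives 57%, 84% and 86%. At 40% versus 20% with 40% ventilated it gives 39%, 59% and 66%. The non-event reading thus costs up to about 7 points over these ranges; the event reading costs far more.

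**Death without ventilation (normal approximation).**
- *Dilution.* Take deaths of 26% versus 8%, assume 10% ventilated survivors in each arm, and assume half of deaths occur unventilated. Ventilation only: 10 + 13 = 23% versus 10 + 4 = 14%, a 9-point difference, power 0.36. Ventilation or death: 36% versus 18%, an 18-point difference, power 0.82.
- *Reversal.* Suppose ventilation-or-death is 35% in both arms, with unventilated deaths 5% on control and 15% on Ampion. The planned endpoint then shows 30% versus 20%, and the test favours Ampion with probability about 0.36: (0.10 − 1.986 × 0.0612)/0.0608 = −0.36, Φ = 0.36. With 10% instead of 15% it is about 0.12. Fisher's exact test, being conservative, gives somewhat lower values.

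**The case against.** The endpoint is called progression throughout both documents, including in the heading and opening sentence of SAP 4.5; *have* occurs only where the parameter is defined. SAP 4.6 varies its verbs in the same way for ICU admission, so this may be loose drafting. If *progress to* governs, the power loss in the table is 0 to 3 points. Deaths are not hidden either: death is score 8 on the primary ordinal scale, and SAP 4.7 gives Day 28 mortality its own test, log-rank comparison and Kaplan-Meier curves. Reporting ventilation and mortality separately is a legitimate choice. The endpoint also stands behind safety, NEWS2, length of stay and oxygen use in the hierarchy, so it may never be formally tested. Finally, efficacy summaries are planned by severity, and the severe stratum should be largely free of patients ventilated at entry.

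Most of this stands as a limit on size. It does not supply the missing rule. Severity summaries are descriptive, and the critical stratum mixes high-flow with ventilated patients. A separate mortality result would reveal an excess of deaths but would not correct this test.

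Three stronger readings are tempting, and the documents do not support them:
- *That patients ventilated at entry will definitely be counted as events, halving the power.* The text conflicts; that loss belongs to one reading only.
- *That counting them biases the comparison.* In expectation they add equally to both arms. This is dilution, with some room for chance imbalance within the critical stratum.
- *That the SAP says deaths are censored in the log-rank test for respiratory failure.* It names death as censoring only for hospital and ICU length of stay (SAP 4.3, 4.6). Censoring here would be the software default, not a stated rule.

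**Conclusion.** The point holds as a gap in specification with a real cost. The plan admits patients who already meet the event, keeps them in the test, and uses conflicting verbs to describe how they count. The risk difference shrinks by the ventilated share on either reading. The loss of power against an at-risk test ranges from negligible to severe: at 30% ventilated, 68% becomes 65% or 33%. That such a range turns on one verb is the reason to settle it before unblinding.

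The treatment of unventilated deaths follows from the event list and the denominator, although the SAP does not say so in words. It can weaken a real effect or create an apparent benefit, by an amount that depends on how many deaths occur without ventilation.

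Every rate used for respiratory failure, the ventilated share and the split of deaths is an assumption, so no single magnitude can be claimed. The primary endpoint is unaffected. The consequence falls on this secondary test and on the ICU and mortality tests after it. Confidence: medium.

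**What to change.** 1. **Reconcile the definition first.** Protocol 5.2 includes high-flow nasal cannula; Protocol 3.3.2 and 9.4.2 and SAP 3.2 and 4.5 do not. Under the wider wording every critical patient would meet the event at entry, so the at-risk set cannot be fixed until the passages agree.
2. **Define the at-risk set.** Under the event list now in SAP 4.5, test progression among randomised patients not on mechanical ventilation, non-invasive ventilation or ECMO at baseline. Use the same set for the log-rank test, and write it as an explicit exception to the all-ITT rule. The restriction rests on baseline status, so the randomised comparison is kept.
3. **Report the others separately.** Summarise worsening on the ordinal scale for patients already ventilated at entry.
4. **State the rule for death.** Count death without ventilation as a failure in this analysis, or at least report ventilation-or-death by Day 28 beside it, and say how death is treated in the log-rank test. Mortality stays a separate endpoint.
5. **Optional.** Stratify the test by severity. This would replace the Fisher test of Protocol 9.4.2 and is not needed to close either gap.

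**Cost.** SAP text alone is not enough: the endpoint is defined in Protocol 3.3.2 and 9.4.2, and Protocol 10.3 requires an approved written amendment. The denominator for this one endpoint falls, for example to 70 per arm if 30% are ventilated at entry. No new data are needed: oxygen mode and ordinal score are recorded at baseline (Protocol 5.1.2). Oxygen mode must be used, because ordinal score 5 combines non-invasive ventilation with high-flow oxygen.

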4.6 Intensive Care

Intensive care is measured by the proportion of participants who require Intensive Care Unit (ICU) admission by Day 28, ICU-free days through Day 28, and ICU LOS from ICU admission to discharge.

There are two endpoints in this set. Hypotheses about both will be tested independently. The first hypothesis about the percentage of patients who are admitted to the ICU involves all patients. The second hypothesis involves only patients who are admitted to the ICU. Since it is not known how many patients will be admitted to the ICU, the testing of the second hypothesis will be considered exploratory and not part of the hierarchical testing scheme

The first hypothesis to be tested is:

$$H_0: \pi_A = \pi_S \text{ versus } H_A: \pi_A \neq \pi_S$$

Where π_A and π_S represent the percentage of patients who are admitted to the ICU for Ampion and Placebo during the first 28 days after randomization. The difference between Ampion and Placebo will be tested via an appropriate chi-square test or Fisher's exact test utilizing PROC FREQ with the EXACT option, if needed.

The second hypothesis to be tested is:

$$H_0: \text{Median}_A = \text{Median}_S \text{ versus } H_A: \text{Median}_A \neq \text{Median}_S$$

Where Median_A and Median_S are the median ICU length of stay for the Ampion and placebo groups through Day 28 and discharge. Assuming there is no censoring, this will be tested using the Wilcoxon rank sum test via PROC NPAR1WAY. If censoring occurs, e.g., death, then the log rank test will be used based on PROC LIFETEST.

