### 9.4.2 Secondary Endpoints

Secondary endpoints assess the effect of inhaled Ampion treatment compared to placebo on the clinical outcomes for participants with respiratory distress due to COVID-19. The secondary endpoints will be tested in a hierarchical manner in the order presented, and thus no adjustment to the alpha level is necessary:

Objective	Endpoint
Secondary	
Assess the effect of Ampion compared to placebo on safety	

Incidence of adverse events (AEs) and serious adverse events (SAEs) from baseline to Day 60.

Assess the effect of Ampion compared to placebo on clinical health	

Change in NEWS2 score from baseline through Day 5.

Change in NEWS2 score from baseline to hospital discharge.

Objective	Endpoint
Assess the effect of Ampion compared to placebo on hospital stay	
 
Hospital length of stay (LOS) from admission to discharge.
 

Assess the effect of Ampion compared to placebo on oxygen use	
 
Change from baseline in oxygen use, blood oxygen saturation, and oxygen flow rate from baseline through Day 5.
 

Assess the effect of Ampion compared to placebo on progression to respiratory failure	
 
Percentage of participants who progress to respiratory failure (i.e., need for mechanical ventilation, ECMO, non-invasive ventilation) by Day 28.
 

Assess the effect of Ampion compared to placebo on intensive care	
 
Percentage of participants who require Intensive Care Unit (ICU) admission by Day 28.
 
ICU-free days through Day 28.
 
ICU LOS from ICU admission to discharge.
 

Assess the effect of Ampion compared to placebo on all-cause mortality	
 
Percentage of participants with a successful outcome (life) or unsuccessful outcome (death) by Day 28.
 

The efficacy endpoints will be evaluated to estimate the treatment effect and use descriptive statistics including mean, standard deviation, percentages, minimum/maximum, and 95% confidence intervals. All endpoints will be tabulated and presented by treatment arm, cohort (moderate and severe), and timepoint. Where appropriate, data will be tabulated and presented cumulatively across cohorts and/or timepoints.

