11.1.2 Efficacy (Analysis population: ITT)

11.1.2.1	Summary and Analysis of Adverse Events (AEs)
11.1.2.2	Summary and Analysis of Change in Blood-oxygen saturation
11.1.2.3	Summary and Analysis of Progression to ARDS
11.1.2.4	Summary of Intensive care unit (ICU)
11.1.2.5	Summary and Analysis of ICU LOS
11.1.2.6	Summary of Hospital LOS
11.1.2.7	Summary of Progression to intubation
11.1.2.8	Summary and Analysis of All-cause mortality and Time to Event
11.1.2.9	Summary of Time to sustained recovery to include pre-hospital status (LOS)
11.1.2.10	Summary of Ordinal scale for clinical improvement

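### ICU length of stay is tested only in patients admitted to ICU, a group treatment can change, while ICU-free days, measurable in everyone, has no test

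*SAP*

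**What the plan says.** SAP 4.6 lists three ICU measures: the proportion admitted by Day 28, then "ICU-free days through Day 28, and ICU LOS from ICU admission to discharge". It goes on: "There are two endpoints in this set". Two hypotheses follow.

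- Admission: "The first hypothesis about the percentage of patients who are admitted to the ICU involves all patients".
- Length of stay: "The second hypothesis involves only patients who are admitted to the ICU". Medians are compared by Wilcoxon rank-sum or, if there is censoring (death is the example given), by log-rank. Because the number admitted is unknown, "the testing of the second hypothesis will be considered exploratory and not part of the hierarchical testing scheme".

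ICU-free days gets neither a hypothesis nor a test.

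Other places bear on this:

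- The ordered secondary list in Protocol 9.4.2 includes "ICU LOS from ICU admission to discharge", after ICU-free days and before mortality, with no exploratory label. SAP section 4 repeats that list.
- The text after both lists assigns length-of-stay endpoints a two-sample t-test.
- SAP 6.1.2: "All efficacy analyses will be performed in the ITT population".
- The ITT efficacy tables in SAP 11.1.2 include "Summary and Analysis of ICU LOS". No row names ICU-free days.

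**The concern.** Randomisation makes the arms comparable as randomised. It does not make the admitted patients of one arm comparable with the admitted patients of the other if treatment affects who is admitted. If Ampion keeps milder patients out of ICU, those still admitted are on average sicker and stay longer. The test could then report longer ICU care for a drug that reduced it.

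The SAP's reason for the exploratory label is an unknown number of patients. That is a point about precision and does not tell the reader that the comparison may be biased. The ICU duration measure that avoids the problem is already an endpoint, but it is the one left without a test. Protocol section 2 says the study will inform decisions on clinical development, so a misleading ICU signal could matter even outside the hierarchy.

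**Working it through.** **Inputs.** The documents give 100 patients per arm, 1:1 allocation, a final alpha of 0.047, and Wilcoxon as the SAP 4.6 test when nothing is censored. They give no ICU rate, stay length or power for any ICU endpoint, so there is no plan figure to reproduce; the stated 80% power concerns mortality. Assumed here: on placebo, 15 short stays averaging 4 days and 15 long stays averaging 12 days per 100; no deaths; no stay lengthened by treatment; all stays within 28 days. Using 0.047 for an exploratory test is also an assumption.

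**Formulas.** With s short and l long stays per 100 patients:

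- mean stay among admitted = (4s + 12l) / (s + l)
- ICU days per randomised patient = (4s + 12l) / 100
- mean ICU-free days = 28 − ICU days per randomised patient

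Placebo: (60 + 180)/30 = 8.0 days among admitted; 240/100 = 2.40 days per randomised patient; 25.60 ICU-free days.

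The last column comes from simulation: admission counts vary binomially, stays follow gamma distributions (shape 6), and the admitted-only Wilcoxon is two-sided at 0.047.

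| Stays prevented by Ampion | Mean stay, admitted | ICU days per randomised | ICU-free days | Trials significant against Ampion |
|---|---|---|---|---|
| none | 240/30 = 8.0 | 2.40 | 25.60 | about 2% |
| 3 short | 228/27 = 8.4 | 2.28 | 25.72 | about 5% |
| 5 short | 220/25 = 8.8 | 2.20 | 25.80 | about 7% |
| 8 short | 208/22 = 9.5 | 2.08 | 25.92 | about 15% |
| 10 short | 200/20 = 10.0 | 2.00 | 26.00 | about 25% |
| 5 short, 5 long | 160/20 = 8.0 | 1.60 | 26.40 | about 2% |

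In the four short-only rows ICU use falls and ICU-free days rise, yet the mean stay among admitted patients increases. If only long stays are prevented (5 of 15), significance against Ampion is under 1% and in its favour about 7%.

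**Sensitivity.** For 10 short stays prevented, gamma shapes from 3 to 20 give 20–29%. Holding admission counts fixed gives 13–17%.

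A second set of assumptions used a control ICU rate of 20–50%, half the stays 1–5 days and half 8–20 days, no deaths, and alpha 0.05. Significantly longer stay on the drug appeared in 5.9–8.6% of trials with a quarter of short stays prevented, 12–25% with half and 28–63% with three-quarters, against about 2.5% with no effect. With half prevented and every remaining stay also cut by one day, it was 5–7%.

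**All-randomised comparison.** With 10 short stays prevented, ranking all 100 patients per arm by ICU days (the same ordering, reversed, as ICU-free days when nobody dies) was significant for Ampion in about 28% of trials and against it in under 0.1%. Under the second set, with half the short stays prevented, a Wilcoxon test of ICU-free days rejected in about 14–25%. The direction is right on average, but power is modest.

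**The case against.** The strongest reply is that SAP 4.6 has already limited the damage. The test is exploratory, and the all-patient admission result stands beside it: with 10 short stays prevented, a reader would see 30% against 20% admitted next to the length-of-stay finding. That stands, and it keeps this from being a threat to the trial's main conclusion. It does not correct the p-value's direction.

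The size depends on which stays are prevented. Equal prevention of short and long stays leaves the test near nominal, and preventing long stays moves it the right way. The critical stratum admits ventilated patients, so some participants may already be in ICU at baseline. Treatment cannot have selected them, and they would dilute the bias; their share is not stated. These limits stand.

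The simulation has no deaths, whereas SAP 4.6 switches to log-rank if deaths censor stays. The percentages therefore describe the Wilcoxon branch only. The log-rank branch uses the same selected patients, so it does not remove the selection.

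A reader might infer that the restriction contradicts the ITT rule. The documents do not support so much. Under Protocol 5.2 ICU length of stay exists only for patients who enter ICU, so SAP 4.6 reads as a specific rule inside a general one. The ITT heading in SAP 11.1.2 is generic and also covers adverse events.

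A reader might also infer from the ordered lists that this test decides whether mortality can be formally tested. SAP 4.6 expressly takes it out of the hierarchy. What remains is an inconsistency between that statement and the lists.

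**Conclusion.** The point holds in a limited form. SAP 4.6 puts a p-value on a comparison that randomisation does not protect, and leaves untested a listed ICU duration endpoint that can be defined for all randomised patients. The exploratory label protects the primary conclusion; what is at risk is a misleading secondary message about ICU care.

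Under the main assumptions the wrong-direction rate runs from about 5% to 25% as 3 to 10 of 15 short stays are prevented, against about 2% by chance. All of this rests on assumed ICU rates and stay lengths and on treatment preventing mainly short stays. Quoting one quarter as the expected error would overstate it: that is the steep end, where two-thirds of short stays and no long stays are prevented.

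This is worth correcting before unblinding, but it does not undermine the trial.

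**What to change.** In SAP 4.6:

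- Recognise all three ICU endpoints. Make ICU-free days through Day 28, in all randomised patients, the tested ICU duration measure, by Wilcoxon rank-sum with deaths by Day 28 given the worst rank.
- Define the calculation, since Protocol 5.2 gives formulas for ICU admission and length of stay but none for ICU-free days. State how a second ICU stay counts.
- Report ICU length of stay among admitted patients by arm, descriptively and without a p-value.

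Then reconcile the rest: the ordered lists in Protocol 9.4.2 and SAP section 4, which still include ICU length of stay; the two-sample t-test wording after both lists; and the SAP 11.1.2 table list, which needs a row for ICU-free days.

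The cost is wording and minor programming. Protocol 5.2 already collects ICU admission and discharge dates, though the documents do not say whether readmissions to ICU are recorded. Many patients will tie at 28 ICU-free days, power will stay modest with 200 patients, and the result will not describe a typical ICU stay; the descriptive table serves that purpose.
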